(j)	х	om		Ň	Noi	?	Y	Y**	Y**
(k)		and	Х——	ast	ıst	?	Ν	Y	Y**
(I)		Ä		Ē	La	x?	Ν	Ν	Y
(m)	?					?	Y***	Y***	Y***
(n)	х	х					Y	Y	Ν
(o)	?	х					Y*	Y	Ν
(p)		х	——Х				Ν	Y	Ν
(q)		х		х			Ν	Y	Ν
(r)				х		Х	Ν	Y	Y
(s)				х		?	Ν	Y	Y**
(t)					х	X	Ν	Ν	Y
(u)					X	?	N	N	Ý
(v)			X		X	·	N	Ŷ	Ŷ

x = start/stop date of medication

? = missing start/stop date of medication

* If a medication is stopped On-treatment or Post-treatment and no start date is recorded it will be assumed that the medication was ongoing from the Pre-treatment phase

** If a medication is started Pre-treatment or On-treatment and no stop date is recorded then usage will be assumed to be ongoing for the remainder of the study *** If a medication has no start or stop date it will be assumed that the medication was ongoing from

the Pre-treatment phase to the Post-treatment phase

200807

10.5. Appendix 5: Data Display Standards & Handling Conventions

10.5.1. Study Treatment & Sub-group Display Descriptors

Treatment Group Descriptions							
	IVWRS Data Displays for Reporting						
Code	Description	Description	Order ^[1]				
A	Dapro	Dapro	1				
В	rhEPO	rhEPO	2				
		Total	3				

NOTES:

1. Order represents treatments being presented in TFL, as appropriate.

10.5.2. Baseline Definition & Derivations

10.5.2.1. Baseline Definitions

For all endpoints (except as noted) the baseline value will be the latest non-missing predose assessment on or before the randomization date. This is generally expected to be the pre-dose value from the Day 1 visit, although such values may be missing.

Parameter	Study Asses	sments Consid	ered As Baseline	Baseline Used in	
	Screen Week -8	Run-in Week -4	Day 1 (Pre-Dose)	Data Display	
Efficacy					
Hgb			Х	Randomization Date	
Monthly IV iron ¹			Х	Randomization Date	
Iron parameters			Х	Randomization Date	
Safety					
Subjects who have in-clinic HD: dry weight, pre-dialysis BP parameters, HR, and weight			X	Randomization Date	
Subjects who have in-clinic HD: post- dialysis BP parameters, HR, and weight		X		Week - 4/Randomization Date	

200807

Parameter	Study Asses	Baseline Used in			
	Screen Week -8	Run-in Week -4	Day 1 (Pre-Dose)	Data Display	
Subjects who do not have in-clinic HD: BP parameters, HR, weight and dry weight			X	Randomization Date	
Lipid parameters, clinical chemistry, hematology, other laboratory, and hepatobiliary (liver) tests			X	Randomization Date	
PRO					
SF-36 domain and component scores			X	Randomization Date	
EQ-5D-5L & VAS			Х	Randomization Date	
PGI-S			Х	Randomization Date	

NOTES:

• Unless otherwise stated, the mean of replicate assessments at any given time point will be used as the value for that time point.

[1] Baseline monthly IV iron dose will be defined as total IV iron (mg) over the 16 weeks prior to randomization. See Section 10.6.3.

[2]: Post-dialysis baseline values for subjects with in-clinic dialysis will be defined as the latest non-missing pre-dose assessment before the randomization date. This will most often be the value recorded at the Week -4 visit. However, for cases where the treatment start date falls after the randomization date, the randomization date will be used as the baseline measurement.

10.5.2.2. Derivations and Handling of Missing Baseline Data

Change from Baseline

Definition	Reporting Details
Change from Baseline	= Post-Baseline Visit Value – Baseline

NOTES:

 Unless otherwise specified, the baseline definitions specified in Section 10.5.2 Baseline Definitions will be used for derivations for endpoints / parameters and indicated on summaries and listings.

• Unless otherwise stated, if baseline data is missing no derivation will be performed and the change from baseline value will be set to missing.

• The baseline definition will be footnoted on all change from baseline displays.

Percent Change from Baseline

Lipid parameters will be log-transformed and the percent change from baseline will be reported. Other endpoints may also be log-transformed if deemed appropriate.

To calculate a geometric mean for baseline measurement or at a specified timepoint, the following steps are used:

- 1. Log-transform the data points
- 2. Calculate the mean and standard error (SE) of the log-transformed data
- Exponentiate the mean, (if required, the mean SE, mean + SE) and the endpoints of the confidence interval back to the original scale in order to obtain the geometric mean, (the geometric mean – SE, the geometric mean + SE) and the confidence interval for the geometric mean.
- 4. Coefficient of variation will be calculated as

$$CV = \sqrt{\exp(Var_{\log scale}) - 1} \times 100\%$$

To calculate a geometric mean for the ratio of a specific timepoint to baseline (expressed as a percent change from baseline), the following steps are used:

- 1. Log-transform the data at both the baseline and the specified timepoint
- 2. For each subject, calculate a change from baseline using the log-transformed data
- 3. Calculate the mean and standard error (SE) of change from baseline using the logtransformed data
- 4. Exponentiate the mean, (if required, the mean SE, the mean + SE), back to the original scale and then subtract 1, then multiply everything by 100% in order to express the geometric mean, (the geometric mean SE, the geometric mean + SE) as the percent change from baseline.

So, geometric mean for percent change from baseline =

[Exp($\sum \{\log(value at specified time point_i) - \log(baseline value_i) \}/n) - 1] x 100,$

Where i = subject, n = total number of subjects, and \sum represents the sum over all subjects.

To calculate a 95% CI of the geometric mean for the ratio of a specific timepoint to baseline (expressed as a percent change from baseline), the following steps are used:

- 1. Log-transform the data at both the baseline and the specified timepoint
- 2. For each subject, calculate a change from baseline using the log-transformed data
- 3. Calculate the mean and standard error (SE) of change from baseline using the logtransformed data
- 4. Calculate the lower and upper limits of the 95% CI of change from baseline using the log-transformed data using standardized normal distribution: Mean -/+ $z(1 \alpha/2)$ *SE

(z for α =0.05 is obtained through PROBIT function in SAS that is specified as PROBIT(0.975))

5. Exponentiate the lower and upper limits of the 95% CI, back to the original scale and then subtract 1, then multiply everything by 100% in order to express the confidence interval (CI) as the percent change from baseline.

To calculate the minimum, median and maximum for the ratio of a specific timepoint to baseline (expressed as a percent change from baseline), the following steps are used:

- 1. Log-transform the data at both the baseline and the specified timepoint
- 2. For each subject, calculate a change from baseline using the log-transformed data
- 3. Calculate the minimum (median and maximum) of change from baseline using the log transformed data.
- 4. Exponentiate the minimum (median and maximum), back to the original scale and then subtract 1, then multiply everything by 100% in order to express the minimum (median and maximum) as the percent change from baseline.

So, minimum percent change from baseline =

[Exp(min {log(value at specified time point_i) - log(baseline value_i) }) - 1] x 100,

Where i = subject.

Unless otherwise specified, the baseline definitions specified in Section 10.5.2 will be used for derivations for endpoints/parameters and indicated on summaries and listings. Unless otherwise specified, if baseline data is missing, no derivation will be performed and the % change from baseline value will be set to missing. The baseline definition will be footnoted on all change from baseline displays.

10.5.3. Reporting Process & Standards

Reporting Process

Software

• The currently supported versions of SAS software, Version 9.4 (or higher) will be used for all analyses unless otherwise specified. Additionally, R Version 3.6.2 or higher may be used for analysis and the production of graphics.

Analysis Datasets

- Analysis datasets will be created according to clinical data interchange standards consortium (CDISC) standards: study data tabulation model (SDTM) implementation guide (IG) Version 3.1.3 with some updates from Version 3.2, Analysis data model (ADaM) IG Version 1.1, and GSK ADaM specification template.
- For creation of ADaM datasets (ADCM/ADAE), the same version of dictionary datasets will be implemented for conversion from system independent (SI) to SDTM.

Generation of RTF Files

• Rich text format (RTF) files will be generated.

200807

Repo	orting Standards
Gene	
C	The current GSK Integrated Data Standards Library (IDSL) will be applied for reporting, unless otherwise stated: 4.03 to 4.23: General Principles
C	 5.01 to 5.08: Principles Related to Data Listings 6.01 to 6.11: Principles Related to Summary Tables 7.01 to 7.13: Principles Related to Graphics
Form	
r • N • T	GSK IDSL Statistical Principles (5.03 & 6.06.3) for decimal places (DP's) will be adopted for eporting of data based on the raw data collected. Numeric data will be reported at the precision collected on the eCRF. The reported precision from non eCRF sources will follow the IDSL statistical principles but nay be adjusted to a clinically interpretable number of DP's.
Plan	ned and Actual Time
•	 scheduled visit days will be used in tables, figures and formal statistical analyses unless otherwise stated. The derived end of treatment value (see Section 10.6.1) will also be included in displays of data by visit. Tables presenting data values by visit will also include values from scheduled visits occurring on or before the Day 1 visit, despite the description contained in the title (e.g., post-randomization, evaluable, or on-treatment). The description in the title refers to the post-randomization values that are included in the table. Reporting for Data Listings: Planned and actual time relative to study drug dosing will be shown in listings (Refer to IDSL Statistical Principle 5.05.1).
Unsc	cheduled Visits
• • •	 Jnscheduled visits will not be included in summary tables, with the following exceptions: If the table includes a row for all post-baseline assessments, unscheduled visits will be included in this row. Some Hgb endpoints will include unscheduled Hgb values (See Section 10.6.3) Some BP endpoints will include unscheduled BP values (see Section 10.6.4) Jnscheduled visits will not be included in figures, with similar exceptions: If the figure includes a data value for all post-baseline assessments, unscheduled visits will be included in this value.
•	If the figure includes a data value for all post-baseline assessments, unscheduled visits will be

200807

Reporting Standards				
Some BP endpoints will include unscheduled BP values (see Section 10.6.4)				
All unscheduled visits will be included in listings.				
Descriptive Summary Statistics				
Continuous Data	Refer to IDSL Statistical Principle 6.06.1			
Categorical Data	N, n, frequency, %			
Graphical Displays				
Refer to IDSL Statistical Principals 7.01 to 7.13.				
Adjusted Means				
 SAS option OBSMARGINS will be used to generate all adjusted mean values, e.g. LSMEANS statement in relevant SAS procedures will include the OBSMARGINS option (or OM as an abbreviation), to weight least square means coefficients of the categorical variables in the model to be proportional to those found in the input dataset. 				

200807

10.6. Appendix 6: Derived and Transformed Data

10.6.1. General

Multiple Measurements at One Time Point

- Mean of the measurements will be calculated and used in any derivation of summary statistics but if listed, all data will be presented.
 - Triplicate BP and HR measurements are expected at certain time points (See Section 10.2.1)
- Subjects having both High and Low values for Normal Ranges at any post-baseline visits for safety parameters will be counted in both the High and Low categories of "Any visit post-baseline" row of related summary tables. This will also be applicable to relevant Potential Clinical Importance summary tables.

Randomization Date

• Date subject was randomized

Treatment Start Date

• First randomized treatment dose start date

Last Non-Zero Dose Date

- Date of last actual dose of randomized study treatment from the IP Discontinuation eCRF form.
 - The dose steps used by the dosing algorithm described in the protocol include a dose hold or a zero dose. If subjects are assigned by the algorithm to a zero dose, they do not receive randomized treatment for that period. Hence, it would be possible for a subject to complete the study, while still following the dosing algorithm, but not be actually taking any actual randomized treatment. The last non-zero dose date, then captures the latest date in the study that a subject physically took a dose of randomized treatment.
- The eCRF allows for the possibility of partial or missing dates to be recorded for the last actual dose of randomized study treatment on the IP Discontinuation form (i.e., missing day, or day and month, or day and month and year). In such a case, or in case of subjects who have a non-missing treatment start date, but are a missing an IP Discontinuation form, the following conventions will be applied in order to impute a last non-zero dose date:
 - Missing day:
 - The last day of the month will be used, unless the treatment stop date also occurs in the same month; in this case, the treatment stop date will be used.
 - Missing day and month;
 - '31' will be used for the day and 'Dec' will be used for the month, unless the treatment stop date also occurs in the same year; in this case the treatment stop date will be used.
 - Missing day, month, and year:
 - Treatment stop date will be used only for subjects who have a nonmissing treatment start date.

200807

Treatment Stop Date				
• •	• Calculated as the latest randomized treatment dose stop date, for subjects who have a non- missing treatment start date. Note that this date could come from a randomized treatment exposure record with a missing or partial dose stop date if the associated dose start date for that exposure record is on or after the last non-missing randomized treatment dose stop date.			
	 '31' will be used for the day and 'Dec' will be used for the month, unless the study completion or withdrawal date also occurs in the same year; in this case, the study completion or withdrawal date will be used. Missing day, month and year: The study completion or withdrawal date will be used only for subjects 			
	who have a non-missing treatment start date.			
End	of Treatment Value			
	 Only defined for subjects with a non-missing treatment start date Hgb, iron, transfusion and PRO parameters: the latest value on or before the treatment stop date + 1 day. Blood pressure, central laboratory, and vital signs parameters: the latest value on or before the last non-zero dose date + 1 day. 			
Stud	ly Completion/Withdrawal Date			
	 Date of withdrawal for subjects withdrawing (i.e., subjects who actively withdraw or are deemed lost to follow-up) from study or date of completion of study for subjects who complete the study. If the date of study withdrawal entered in the eCRF is before the last study contact date, the last study contact date will be used as the study withdrawal date for analysis. 			
	 Note: Subjects who die while on study are considered as having completed the study 			
	 The eCRF allows for the possibility of missing or partial dates to be recorded for the study completion/withdrawal date on the Study Conclusion form (i.e., missing day, or day and month, or day and month and year). In such a case, or in case of subjects who are missing a Study Conclusion form, the following conventions will be applied in order to impute a study completion/withdrawal date: Missing day: 			
	 The last day of the month will be used, unless the last study contact date also occurs in the same month; in the case, the last study contact date will be used. 			

200807

the last study contact date also or last study contact date will be use	Dec' will be used for the month, unless ccurs in the same year; in this case, the ed.
 Missing day, month and year: The last study contact date will be 	
Planned/Actual Visit Dates	
Planned/actual visit dates will be defined as follow	
 Week 28 date: Non-missing Week 28 visit randomization date + 28*7 	t start date (from SV domain), otherwise
 Week 36 date: Non-missing Week 36 visit randomization date + 36*7 	t end date (from SV domain), otherwise
 Week 52 date: Non-missing Week 52 visit randomization date + 52*7 	t end date (from SV domain), otherwise
 End of Study date: Non-missing End of Study otherwise the middle of the End of Study 	
Stabilization Period	
 Defined as the period between and including the r visit, using planned/actual dates. 	andomization date + 1 day - <week 28<="" td=""></week>
Alternative Evaluation Period (Alt. EP)	
 Defined as the period between and including Wee planned/actual dates. 	ek 28 visit – Week 36 visit, using
Evaluation Period (EP)	
 Defined as the period between and including Wee planned/actual dates. 	ek 28 visit – Week 52 visit, using
Maintenance Period (MP)	
 Defined as the period between and including Wee planned/actual dates. 	k 28 visit – End of Study visit, using

200807

St.	udy Day				
•	 Calculated as the number of days from randomization date: Ref Date = Missing → Study Day = Missing 				
	5 , , 5				
	 Ref Date < Randomization Date → Study Day = Ref Date - Randomization Date Ref Date > Randomization Date → Study Day = Ref Date - (Randomization Date) + 1 				
T	• Ref Date ≥ Randomization Date → Study Day = Ref Date – (Randomization Date) + 1				
Ire	eatment Day				
•	Calculated as the number of days from treatment start date:				
	Treatment Start Date = Missing → Treatment Day = Missing				
	• Ref Date < Treatment Start Date \rightarrow Treatment Day = Ref Date – Treatment Start Date				
	 Ref Date ≥ Treatment Start Date → Treatment Day = Ref Date – (Treatment Start 				
1.5	Date) + 1 st Study Contact Date				
	-				
•	Latest visit date from an unscheduled visit or a clinic, telephone, designated third party, healthcare provider or medical records, other, or other contact with subject (mail, email, text,				
	social media, etc.) visit.				
Tin	ne Definitions (per GSK standard principles)				
•	1 week = 7 days				
•	1 month = 30.4375 days				
•	1 year = 365.25 days				
Pro	oduction of Two-Sided p-values				
•	 The majority of the efficacy and safety analyses in this study will use one-sided 2.5% p-values to assess statistical significance. Should two-sided p-values be required for publication purposes after the study is complete, the corresponding two-sided p-values will be produced at that time. 				
La	st Known Alive Date				
•	The last know alive date for a subject in the study will be defined as the latest of the following dates:				
	 The date of the last visit in the clinic 				
	 Last date recorded when the subject was last known alive 				
	 For the non-clinic visit, the last clinic information assessment date 				
10	0.6.2. Study Population				
10	.6.2.1. Subject Disposition				
Subject Disposition					
Sc	reen Failures				
•	Screen failures are defined as subjects who consent to participate in the clinical trial but are no subsequently randomized.				
	 At the time of screening closure, there may have been subjects who had been consented but had not been entered into the eCRF. These subjects are not included in the clinical database but will be noted in a footnote on the Summary of Screening Status and Beesens for Screen Failures. 				

Screening Status and Reasons for Screen Failures.
Any subject that consented, was entered into the eCRF, and was not randomized, but is

			200807			
0		- 141				
Subject Disposition						
	-	creen failure record will have the following values imputed:				
	0	Was this subject a screen failure? = Yes				
Don	0 T borimol	Reason for screen failure = Missing reatment Discontinuation				
)			
		nized subject with a non-missing treatment start date that is missing an IF ition eCRF will have the following values imputed:	,			
	0	Date of last dose = See Last Non-Zero Dose Date in Section 10.6.1				
	0	Was the study treatment stopped permanently before the scheduled end treatment period? = Yes	l of the			
	0	Primary reason the treatment was stopped = Missing				
Stu	dy Complet	ters/Withdrawals				
	Any randon imputed:	nized subject that is missing Study Conclusion eCRF will have the following	ng values			
	0	Date of subject completion or withdrawal? = See Study Completion/With Date in Section 10.6.1	drawal			
	0	Was the subject withdrawn from the study? = Yes				
	0	Primary reason for study withdrawal = Missing				
		· · · ·				
Sub	jects Com	oletion Status				
Kno	wn Cardio	vascular Endpoint Status at End of Study				
The	following so	cenarios will be considered as known CV endpoint status at End of Study	:			
	•	no die during the study				
	•	no attend a clinic visit within the EOS window				
	,	owing non-clinic EOS visits, eCRF Visit Contact Details page indicates that	at a clinical			
	events asse	essment was able to be performed and date clinical information was asse				
	0	Telephone contact with subject				
	0	Other contact with subject (mail, email, text, social media, etc.)				
	0	Designated third party (e.g. family member, caretaker)				
	0	Health care provider or medical records				
Unk	nown Card	liovascular Endpoint Status at End of Study				
The	following so	cenarios will be considered as incomplete CV endpoint status at End of S	tudy:			
•	Subjects wh	no withdraw from the study	-			
•	EOS visit ty	ipe =				
	0	no contact able to be made for this visit				
	0	survival status search performed but could not confirm that the subject w	vas alive			
		or dead				
	0	Publicly available sources (e.g., public registry, newspaper)				
	0	Other, specify				
	events asse	owing non-clinic EOS visits, eCRF Visit Contact Details page indicates the essment was not able to be performed or date clinical information was as EOS window:				
	0	Telephone contact with subject				
L	~	· · · · · · · · · · · · · · · · · · ·				

200807

	pletion Status
0	Other contact with subject (mail, email, text, social media, etc.)
0	Designated third party (e.g. family member, caretaker)
0	
	Contact Details page is missing information to determine if a clinical events at was performed or the date it was performed.
Known Vital S	tatus at End of Study
The following s	cenarios will be considered as known vital status at End of Study:
 Subjects w 	ho die during the study, or have a death date
Subjects w	ho attend a clinic visit within the EOS window
For the foll	owing non-clinic EOS visits, latest date subject last known to be alive is within or OS window.
0	Telephone visit
0	Other contact with subject (mail, email, text, social media, etc.)
0	Designated third party (e.g. family member, caretaker)
0	Health care provider or medical records
0	Publicly available sources (e.g., public registry, newspaper)
0	Other, specify
•	ts who withdraw from the study, the latest date subject last known to be alive is iter the EOS window.
Jnknown Vita	I Status at End of Study
	cenarios will be considered as unknown vital status at End of Study:
 For subject 	ts who withdraw from the study, the latest date subject last known to be alive is before the EOS window;
-	ype = no contact able to be made for this visit (LTFU subjects only);
EOS visit t	ype = survival status search performed but could not confirm that the subject was ad (LTFU subjects only);
	owing non-clinic EOS visits, latest date subject last known to be alive is missing or EOS window.
0	Telephone visit
0	Other contact with subject (mail, email, text, social media, etc.)
0	Designated third party (e.g. family member, caretaker)
0	Health care provider or medical records
0	Publicly available sources (e.g., public registry, newspaper)
	Other, specify

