10.4. Appendix 4: Treatment States and Phases

10.4.1. Treatment States

Assessments and events will be classified according to time of occurrence relative to the treatment start and stop dates and last non-zero dose date (see Section 10.6.1).

10.4.1.1. Treatment States for Hgb, Iron Parameters, IV Iron Dose Endpoints, Iron Use Summaries, Transfusion and PRO Data

Treatment State	Definition
Pre-Treatment	Date ≤ Treatment Start Date
On-Treatment	Treatment Start Date < Date ≤ Treatment Stop Date + 1 day
Post-Treatment	Date > Treatment Stop Date + 1 day
Post-Randomization	Randomization Date < Date

NOTES:

• If the treatment stop date is missing and the treatment start date is non-missing and Date > Treatment Start Date, then the assessment will be considered to be On-Treatment

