 define For standard For standard 	eriod for treatment discontinuation begins at randomization. The end of this time period is ed as follows: or subjects who did not take randomized treatment, use the date of randomization or subjects whose treatment stop date is missing and who took randomized treatment, use cudy conclusion date or subjects either continuing on study past treatment stop date or completing/withdrawing on the same day as treatment stop date, use treatment stop date
Any e perioc	vents that occurred before the start of this time period are considered to be prior to the time d for treatment discontinuation, and any endpoints that occurred after the end of this time d are considered to be post the time period for treatment discontinuation.

200807

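### When the final exposure stop date is missing, Treatment Stop Date is imputed from study completion or withdrawal without using the last-dose date on the IP Discontinuation form, which lengthens the on-treatment window for IV iron to Week 52 and a few other endpoints

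*SAP*

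**What the plan says.** Section 10.6.1 of the SAP defines two end-of-treatment dates from two sources.

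- **Last Non-Zero Dose Date** is the "Date of last actual dose of randomized study treatment from the IP Discontinuation eCRF form". If that date is wholly missing, "Treatment stop date will be used only for subjects who have a nonmissing treatment start date".
- **Treatment Stop Date** is "Calculated as the latest randomized treatment dose stop date, for subjects who have a non- missing treatment start date". The section notes that "this date could come from a randomized treatment exposure record with a missing or partial dose stop date", provided that record starts on or after the last known stop date. If day, month and year are all missing, "The study completion or withdrawal date will be used only for subjects" with a non-missing treatment start date. If the year alone is known, 31 December is used, or the completion or withdrawal date when it falls in that year.

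Borrowing therefore runs one way: a missing last dose can take the treatment stop date, but a missing treatment stop date does not take the last dose. The section gives the reason for keeping the dates apart: "If subjects are assigned by the algorithm to a zero dose, they do not receive randomized treatment for that period", so a subject can be following the dosing algorithm without taking drug.

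**The concern.** Study completion is a poor stand-in for the end of treatment in this trial. Section 10.7.1 says that subjects who stop study drug early are encouraged to stay in the study, and section 10.2.1.3 gives them a visit schedule through to End of Study. For such a subject the completion date can fall long after the last dose, and the plan already collects a better date on the IP Discontinuation form.

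The rescue endpoint shows this most plainly. Under 10.6.3.3 the event is identified by the recorded reason and subreason for stopping treatment, but it is dated by Treatment Stop Date. Section 10.6.2.1 shows that the IP Discontinuation form holds both the reason for stopping and the date of last dose. With an open final exposure record, the reason would be accepted while the last-dose date is passed over.

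The most important analysis exposed is the average monthly IV iron dose to Week 52, one of the four multiplicity-controlled principal secondary tests (10.11.1.2). Section 8.1.1.2 intends its window to be time on randomized treatment before any transfusion.

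**Working it through.** The plan states no sample size, power or event count that depends on this rule, so there is no figure to reproduce. The check is a trace of where each date is used, followed by an illustration.

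**1. Which window uses which date**

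| Data or endpoint | End of window | SAP section | Affected? |
|---|---|---|---|
| Hgb, iron, IV iron, transfusion, PRO | Treatment Stop Date + 1 day | 10.4.1.1 | Yes, by rule |
| IV iron to Week 52 | earliest of Week 52, first transfusion, Treatment Stop Date + 1 | 8.1.1.2 | Yes |
| Months of exposure | Treatment Stop Date | 10.6.2.5 | Yes |
| Time to treatment discontinuation | Treatment Stop Date | 10.6.2 | Yes |
| Time to rescue | Treatment Stop Date | 10.6.3.3 | Yes |
| On-treatment CV endpoints | Last Non-Zero Dose Date + 28 days | 10.4.1.2, 10.6.4.1 | No |
| BP, laboratory, vital signs | Last Non-Zero Dose Date + 1 day | 10.4.1.3 | No |
| Treatment-emergent AEs | Last Non-Zero Dose Date + 1 day | 10.4.1.4 | No |
| Co-primary Hgb | on- and off-treatment values | 7.1.2.4 | No |
| Co-primary MACE | study completion or withdrawal | 10.6.4.1 | No |

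The rows marked No assume that the form carries the last-dose date, which is the case at issue.

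**2. Illustration.** All days are assumptions: treatment start and randomization on Day 1, Week 52 visit on Day 365, no transfusion, final exposure record with no stop date, study completion on Day 900. Let S be the Treatment Stop Date. From 10.6.3.2:

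IV iron months = [min(S + 1, 365) − 1 + 1] / 30.4375

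- Rule as written, S = 900: 365 / 30.4375 = 11.99 months.
- Form date used, S = 120: 121 / 30.4375 = 3.98 months.
- Ratio: 121 / 365 = 0.33.

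| Last dose on form | Months with form date | Months as written | Ratio |
|---|---|---|---|
| Day 60 | 2.00 | 11.99 | 0.17 |
| Day 120 | 3.98 | 11.99 | 0.33 |
| Day 200 | 6.60 | 11.99 | 0.55 |
| Day 300 | 9.89 | 11.99 | 0.82 |

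The ratios are the same for completion on Day 600, 900 or 1200, because each lies beyond Day 365.

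For the Day 120 subject:

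- Exposure is 900 / 30.4375 = 29.6 months instead of 120 / 30.4375 = 3.9.
- The Hgb window ends on Day 901 instead of Day 121.
- A rescue stop is dated Day 900 instead of Day 120.
- The on-treatment CV window ends on Day 120 + 28 = 148 under either rule.

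**3. How much off-treatment data can enter.** Section 10.2.1.3 schedules discontinued subjects at Weeks 28, 40 and 52 within the evaluation period, so a subject who stopped before Week 28 has at most three of the seven scheduled Hgb values. Section 10.6.3.1 also removes values within 8 weeks after a transfusion or non-randomized ESA. PRO questionnaires and iron parameters are scheduled only at the discontinuation visit. IV iron and transfusions are still recorded at the Year 1 visits.

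**The case against.** Four counter-arguments deserve weight.

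- **Two dates are deliberate.** Windows that end on different days are not in themselves a contradiction, because dose holds justify separate dates. This stands, and it limits the fix. It does not justify study completion as the end of treatment for someone whose permanent stop is recorded.
- **Rarity.** The rule acts only when the undated record starts on or after the last known stop date. Sites complete an exposure record at nearly every dosing instruction (10.6.3.6), and data cleaning precedes unblinding (3.2). This stands. The SAP gives no frequency, and the effect at arm level is probably small.
- **Legibility.** Some lines of the Treatment Stop Date entry, including any missing-day rule, cannot be read in the available text, so a further condition cannot be excluded. The rule for a fully missing date is legible, and its only visible condition is a treatment start date.
- **Limited reach.** A reader might infer that the subject counts as on treatment to study end throughout the report. The table above shows otherwise. A reader might also infer that all seven evaluation-period Hgb values become evaluable and contaminate the per-protocol analysis. At most three are scheduled for a subject who stops before Week 28, and per-protocol exclusion 02 (10.1.1) covers fewer than five of seven, which largely removes that effect.

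**Conclusion.** The point holds for endpoints built on Treatment Stop Date. For a subject with an open final exposure record who stopped early and remained in follow-up, the stated rule gives too late an end of treatment although a better date may be on file. The main exposure is IV iron to Week 52. Months of exposure, time to treatment discontinuation, the rescue date, transfusion rates and a few evaluable Hgb values are also exposed. Both co-primaries, on-treatment MACE, treatment-emergent AEs, BP and laboratory data are not.

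The size per subject can be large, as the illustration shows, but the days are assumed and the number of such subjects is unknown. The ratios describe the averaging period, not the dose: IV iron given after stopping would enter the numerator too. A reader might infer a known bias in the treatment comparison. The document supports neither a direction nor a size for that, because it does not say how such records would fall between the arms.

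**What to change.** Add one rule to the Treatment Stop Date entry in 10.6.1. When the final exposure record's stop date is missing or partial, and the IP Discontinuation form records permanent discontinuation with a complete last-dose date, use that date as the upper limit for the imputed Treatment Stop Date, but not earlier than the record's start date.

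Keep the current imputation in three cases:

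- the form's date is missing or partial;
- treatment was not permanently discontinued early;
- the open record is an IRT-assigned dose hold (zero dose), where the last dose comes before the record and a cap would remove time on the algorithm.

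No change is needed to the fallback in 10.4.1.1 ("If the treatment stop date is missing and the treatment start date is non-missing and Date > Treatment Start Date") or the one in 10.6.3.3 ("subjects whose treatment stop date is missing and who took randomized treatment, use" the study conclusion date), because 10.6.1 already imputes a stop date for every treated subject. The cost is a short addition to the SAP and one merge in programming, with no new data.
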